Neonatal medical history will include birth/termination outcome (live birth, stillbirth, termination/miscarriage, neonatal death), demographics, physical examination, overall Apgar score, weight, length, head circumference, key findings of fetal monitoring during labor such as fetal presentation at delivery, gestational age, complications, fetal heart rate and uterine contractions during labor.

All AEs and special reporting situations, whether serious or non-serious, that are related to study procedures or that are related to non-investigational sponsor products will be reported for all participants (adult participants and neonates/infants) from the time a signed and dated informed consent form (ICF) is obtained until the end of the study/early withdrawal.

For adult participants, solicited AEs, collected through a reactogenicity diary as part of the eCOA, will be recorded from the time of vaccination until 7 days post-vaccination (or until resolution). All other unsolicited AEs and special reporting situations, whether serious or non-serious, will be reported from the time of vaccination until 28 days post-vaccination.

Subjective changes in (postpartum) breast milk production (reduction) will be collected in the eCOA diary.

All SAEs, AESI and AEs (including pregnancy-related AEs, throughout pregnancy) leading to discontinuation from the study/vaccination (regardless of the causal relationship) are to be reported for all adult participants from the moment of vaccination until completion of the participant's last study-related procedure. The investigator's assessment of ongoing AEs at the time of each participant's last visit should be documented and closed in the participant's medical record.

SAEs and AESIs in the neonates/infants will be followed up from birth until 12 months postpartum. MAAEs are to be reported for all adult participants from the moment of vaccination until 6 months after vaccination. MAAEs leading to study discontinuation (for both adults and neonates/infants), are to be reported during the entire study.

Plasma and serum derived from whole blood samples will be collected from all participants for retrospective analysis of hematological parameters, including pro- and anti-coagulation factors (see Section 8.2.3.1), in the event of a suspected AESI of thrombosis with thrombocytopenia syndrome (TTS) post-vaccination.

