3. OBJECTIVES AND ENDPOINTS

Objectives	Endpoints
Primary	
To assess the safety and reactogenicity of Ad26.COV2.S administered intramuscularly (IM) as a 1-dose (5×10^{10} vp) schedule in adult participants, during the 2 nd and/or 3 rd trimester of pregnancy, and (potentially) postpartum.	
 • Solicited local and systemic AEs for 7 days after vaccination, or until resolution. • Unsolicited AEs for 28 days after vaccination. • SAEs and AESI throughout the study (from vaccination until end of the study, ie, at least 12 months after delivery). • MAAEs until 6 months after vaccination. • AEs leading to study discontinuation (during the entire study).
To assess the humoral immune response in peripheral blood of adult participants to Ad26.COV2.S administered IM as a 1-dose (5×10^{10} vp) schedule, during the 2 nd and/or 3 rd trimester of pregnancy, 28 days after vaccination.	
 • Serological response to vaccination as measured by ELISA; [S-ELISA, EU/mL]), 28 days after vaccination.
Secondary	
Adults	
To assess safety of the booster dose of Ad26.COV2.S at 5×10^{10} vp on participants who were vaccine naïve at study entry.	
 • Solicited local and systemic AEs for 7 days after booster vaccination, or until resolution. • Unsolicited AEs for 28 days after vaccination. • SAEs and AESI throughout the study (from vaccination until end of the study, ie, at least 12 months after delivery). • MAAEs until 6 months after vaccination. • AEs leading to study discontinuation (during the entire study).
To assess pregnancy outcomes in adult participants who have received Ad26.COV2.S during the 2 nd and/or 3 rd trimester of pregnancy.	
 • Pregnancy outcomes (including, live term birth, live preterm birth, stillbirth, and abortion) (non-exhaustive).
To assess pregnancy-related AEs in adult participants who have received Ad26.COV2.S during the 2 nd and/or 3 rd trimester of pregnancy.	
 • Pregnancy-related AEs throughout pregnancy (including gestational diabetes, gestational hypertension, premature rupture of membranes, premature labor, premature uterine

	contractions, poor or restricted fetal growth, pre-eclampsia, eclampsia, vaginal or intrauterine hemorrhage) (non-exhaustive).

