Any solicited local or systemic AEs, unsolicited AEs, SAEs, AESI, pregnancy-related AEs throughout pregnancy, MAAEs, concomitant medications, and vital signs will be documented by study site personnel following this observation period. In addition, adult participants will record solicited signs and symptoms in a reactogenicity diary for 7 days post-vaccination.

The reporting periods of unsolicited AEs, SAEs, AESI, pregnancy-related AEs throughout pregnancy, MAAEs, and special reporting situations are detailed in Section 8.3. Reporting periods for concomitant therapy are outlined in Section 6.8.

In addition, participants will be asked daily if they have experienced any health concerns (including new onset of symptoms such as shortness of breath, chest pain, leg swelling, persistent abdominal pain, severe or persistent headaches or blurred vision, easy bruising, or tiny blood spots under the skin beyond the site of the injection) within the 30-day time period post-vaccination, and if so, participants will be advised to contact the study center. For Group 4 booster participants only, subjective changes in (postpartum) breast milk production (reduction) will be collected in the eCOA diary.

Adverse maternal/fetal outcomes and adverse neonate/infant outcomes SAEs (including MIS-C), MAAEs and AEs leading to discontinuation will be recorded. A final safety follow-up visit is scheduled 12 months postpartum for adult participants and approximately 12 months after birth for the neonates/infants.

From all adult participants and neonates/infants, blood samples will be collected at selected timepoints indicated in the Schedules of Activities in Section 1.3, for humoral immunogenicity assessments, with an emphasis on neutralizing and binding antibody responses. In addition, blood

samples will be collected at selected timepoints indicated in the Schedules of Activities in Section 1.3; analysis of vaccination-related biomarkers in PAXgene® tubes may be performed.

From a subset of approximately 25 adult participants per group, PBMCs were to be collected for analysis of cellular immunogenicity (including Th1/Th2 assessments). With only 1 participant in this subset at the time of writing this Protocol Amendment 7, PBMC sampling will be removed from the study as of Protocol Amendment 7 approval.

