All AEs and special reporting situations, whether serious or non-serious, that are related to study procedures or that are related to non-investigational sponsor products will be reported for all participants (adult participants and neonates/infants) from the time a signed and dated ICF is obtained until the end of the study/early withdrawal.

Clinically relevant medical events not meeting the above criteria and occurring between signing of the ICF and moment of first vaccination will be collected on the Medical History eCRF page as pre-existing conditions.

For adult participants, solicited AEs, collected through a reactogenicity diary as part of the eCOA, will be recorded for vaccination from the time of vaccination until 7 days post-vaccination (or until resolution).

All other unsolicited AEs and special reporting situations, whether serious or non-serious, will be reported from the time of vaccination until 28 days post-vaccination. Unsolicited AEs with the onset date outside the timeframe defined above (>28 days after previous study vaccination), which are ongoing on the day of the subsequent vaccination, should be recorded as such.

All SAEs, AESI, AEs and pregnancy-related AEs throughout pregnancy leading to discontinuation from the study/vaccination (regardless of the causal relationship) are to be reported for all adult participants from the moment of first vaccination until completion of the participant's last study-related procedure, which may include contact for safety follow-up. The investigator's assessment of ongoing AEs at the time of each participant's last visit should be documented and closed in the participant's medical record. The sponsor will evaluate any safety information that is spontaneously reported by an investigator beyond the time frame specified in the protocol.

MAAEs are defined as AEs with medically-attended visits including hospital, emergency room, urgent care clinic, or other visits to or from medical personnel for any reason. Routine study visits will not be considered medically-attended visits. New onset of chronic diseases will be collected as part of the MAAEs. MAAE are to be reported for all participants from the moment of the vaccination until 6 months after vaccination. MAAEs leading to study discontinuation which are to be reported until completion of the participant's last study-related procedure. New onset of chronic diseases will be collected as part of the MAAEs.

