10.4.5. Procedures

All Adverse Events

All AEs (including pregnancy-related AEs throughout pregnancy), regardless of seriousness, severity, or presumed relationship to study vaccination, must be recorded using medical terminology in the source document and the eCRF. Whenever possible, diagnoses should be given when signs and symptoms are due to a common etiology (eg, cough, runny nose, sneezing, sore throat, and head congestion should be reported as "upper respiratory infection"). Investigators must record in the eCRF their opinion concerning the relationship of the AE to study therapy. All measures required for AE management must be recorded in the source document and reported according to sponsor instructions.

For all studies with an outpatient phase, including open-label studies, the participant must be provided with a "wallet (study) card" and instructed to carry this card with them for the duration of the study indicating the following:

- Study number
- Statement, in the local language(s), that the participant is participating in a clinical study
- Investigator's name and 24-hour contact telephone number
- Local sponsor's name and 24-hour contact telephone number (for medical personnel only)
- Site number
- Participant number

Serious Adverse Events

All SAEs (including pregnancy-related AEs throughout pregnancy), that have not resolved by the end of the study, or that have not resolved upon the participant's discontinuation from the study, must be followed until any of the following occurs:

- The event resolves
- The event stabilizes
- The event returns to baseline, if a baseline value/status is available
- The event can be attributed to agents other than the study vaccine or to factors unrelated to study conduct
- It becomes unlikely that any additional information can be obtained (participant or health care practitioner refusal to provide additional information, lost to follow-up after demonstration of due diligence with follow-up efforts)

Suspected transmission of an infectious agent by a medicinal product will be reported as an SAE. Any event requiring hospitalization (or prolongation of hospitalization) that occurs during participation in the study must be reported as an SAE, except hospitalizations for the following:

- Hospitalizations not intended to treat an acute illness or AE (eg, social reasons such as pending placement in long-term care facility)

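### The reporting rule in Section 8.3.1 and the synopsis ties pregnancy-related AEs to discontinuation, contradicting the secondary endpoint and leaving a narrow class of events after Day 28 without a stated collection period

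*Protocol*

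**What the plan says.** The secondary endpoint in Section 3 is "Pregnancy-related AEs throughout pregnancy (including gestational diabetes, gestational hypertension, premature rupture of membranes, premature labor, premature uterine" contractions and other listed conditions. It is not restricted to serious events or to events that end participation. Section 9.2.2 lists these events as a monitoring item of their own, and Section 9.4.2 plans an analysis of them by group and overall.

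For timing, Section 4.1 (Study Procedures) says: "The reporting periods of unsolicited AEs, SAEs, AESI, pregnancy-related AEs throughout pregnancy, MAAEs, and special reporting situations are detailed in Section 8.3". Section 8.3.1 then gives these periods for adults:

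- Unsolicited AEs, serious or not: "will be reported from the time of vaccination until 28 days post-vaccination".
- Until the last study-related procedure: "All SAEs, AESI, AEs and pregnancy-related AEs throughout pregnancy leading to discontinuation from the study/vaccination", regardless of causality.
- Medically attended AEs: "MAAE are to be reported for all participants from the moment of the vaccination until 6 months after vaccination". Routine study visits do not count as medical attendance.

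The synopsis (Safety Assessments) words the second item as "All SAEs, AESI and AEs (including pregnancy-related AEs, throughout pregnancy) leading to discontinuation from the study/vaccination". Section 10.4.5 takes a wider line: "All AEs (including pregnancy-related AEs throughout pregnancy), regardless of seriousness, severity, or presumed relationship to study vaccination, must be recorded" in the source document and the eCRF.

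**The concern.** In Section 8.3.1 the discontinuation condition directly follows the pregnancy-related AEs and reads naturally as qualifying them. In the synopsis they stand in brackets inside the AEs that lead to discontinuation, which leaves less room for another reading. Section 8.3.1 names pregnancy-related AEs in its heading but gives no other period for them as a class. The period that the endpoint needs is therefore not stated where the protocol says it will be found.

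A site that follows the sentence as written could leave out some non-serious gestational events after the 28-day window, while a site that follows Section 10.4.5 would record them. The reported frequency would then depend partly on how each site reads one sentence. The preferred-term list that Section 9.4.2 leaves to the SAP cannot repair this, because it can only select from events that were collected.

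**Working it through.** The protocol gives no figure for this point, so there is none to reproduce. The check sets the provisions side by side and then does simple date arithmetic.

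**Which text sets the period**

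- Section 4.1 points to Section 8.3. The note in Section 10.4.1 (Appendix 4) and footnote t of the adult Schedules of Activities point to Section 8.3.1.
- Section 10.4.5 says what must be recorded, not for how long. Read alone as a timing rule, it would also override the 28-day window for every other AE, so it cannot serve as one.
- The AE/SAE/AESI/MAAE row in the Schedules is marked as continuous. In Section 1.3.1 the unsolicited-AE row carries the same mark, yet footnote r limits it to 28 days. The mark alone does not set a period.

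**What is collected after Day 28**

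- SAEs and AESIs: to the end of the study, under their own paragraphs of Section 8.3.1.
- AEs leading to discontinuation: throughout the study.
- Medically attended AEs, serious or not: to 6 months after vaccination.
- Adverse maternal and fetal outcomes: continuously, under both adult Schedules. Section 9.4.2 summarises these under Outcomes, separately from the pregnancy-related AEs.

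**Time covered**

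Inputs: vaccination at week 16 to week 38 (inclusion criterion 6); a 28-day unsolicited window; a 6-month window for medically attended AEs, taken as 182 days. Delivery at week 40 or 42 is an assumption.

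Days from vaccination to delivery = 7 × (delivery week − vaccination week). Days after the window = that number − 28, or 0 if negative.

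| Vaccination week | Delivery week | Days to delivery | Days after the 28-day window | Share of time | Within 182 days? |
|---|---|---|---|---|---|
| 16 | 40 | 168 | 140 | 83% | yes |
| 16 | 42 | 182 | 154 | 85% | yes |
| 28 | 40 | 84 | 56 | 67% | yes |
| 32 | 40 | 56 | 28 | 50% | yes |
| 36 | 40 | 28 | 0 | 0% | yes |
| 38 | 40 | 14 | 0 | 0% | yes |

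The longest case, week 16 to week 42, is 7 × 26 = 182 days, so the medically attended window reaches delivery in every row. The shares are shares of calendar time, not of events.

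**What is left over**

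Removing the covered categories leaves pregnancy-related AEs after Day 28 that are non-serious, not AESIs, not medically attended, not leading to discontinuation and not otherwise captured as a maternal/fetal outcome. Two routes lead there:

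- The scheduled contacts between Visit 5 and delivery are monthly phone calls. An event told only to site staff on such a call, for example premature contractions for which no care was sought, has no explicit rule.
- An event found only at a routine study visit is not medically attended by definition. Visit 5 is Day 29 ± 7 days, so it can fall up to 7 days after the 28-day window, and Visit 9 takes place at pregnancy completion.

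**The case against.** The strongest reply is that the sentence in Section 8.3.1 cannot be meant literally. If the discontinuation condition governed the whole list, it would restrict SAEs and AESIs too, and the same section contradicts that. The words on the duration of pregnancy could then be read as giving this class its own period. Sections 1.1, 2.3.3, 4.1 and 9.2.2 also speak of recording, documenting or monitoring these events with no discontinuation condition. Most of the listed conditions, such as gestational diabetes, gestational hypertension or restricted fetal growth, need testing or measurement. Between Visit 5 and delivery that would normally happen in non-study care, which makes the event medically attended.

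Much of this stands. It rules out the stronger reading that a reader might infer, that non-serious events after Day 28 need not be reported at all: medically attended ones must be, and that window reaches delivery. Nor is that window the only safeguard, since maternal and fetal outcomes are recorded continuously and the delivery history (Section 8.2.4) captures rupture of membranes and delivery complications.

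It does not remove the contradiction. SAEs and AESIs have separate paragraphs in Section 8.3.1 that restore their period; pregnancy-related AEs have none. The general statements elsewhere either give no reporting rule or refer back to Section 8.3. The synopsis wording is hard to read in any other way. That the listed conditions usually come to medical attention is a reasonable judgement, but the protocol does not say so.

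**Conclusion.** The point holds as a contradiction in the collection rule for a named secondary endpoint, with a limited practical gap. Section 8.3.1 and the synopsis do not match Section 3, Section 9.4.2 or Section 10.4.5. The events without a stated period are the residual class set out above.

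The number of events affected cannot be derived from the document. A reader might take the 83%, 67% or 50% of time after the 28-day window as the share of events lost. That inference is not supported: most events in that time are probably caught by other rules, and the share is 0% for vaccination at week 36 or later with delivery at week 40. Nor is a downward bias shown; what can be said is that collection may be inconsistent between sites.

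The analysis is descriptive and enrollment has ceased, so no test or threshold is at stake. Enrolled participants are still followed, however, and with the limited sample size that the protocol acknowledges, a few events recorded or not could move a reported percentage. The time calculation rests on the assumed delivery weeks and on 6 months taken as 182 days.

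**What to change.** Reconcile the synopsis and Section 8.3.1 with Sections 3 and 10.4.5 by splitting the sentence in both places:

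- SAEs, AESIs and AEs leading to discontinuation from the study or from vaccination are reported until the participant's last study-related procedure.
- All pregnancy-related AEs, serious or not and whether or not they lead to discontinuation, are reported from vaccination until pregnancy completion or termination.

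Add a matching line to the eCRF completion guideline, so that events mentioned on the monthly calls or found at study visits are entered. The cost is one sentence in two places, that line and a few more AE records. Only data collection changes; clinical management does not.

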8.3.4. Regulatory Reporting Requirements for Serious Adverse Events

The sponsor assumes responsibility for appropriate reporting of AEs to the regulatory authorities. The sponsor will also report to the investigator (and the head of the investigational institute where required) all suspected unexpected serious adverse reactions (SUSARs). The investigator (or sponsor where required) must report SUSARs to the appropriate IEC/IRB that approved the protocol unless otherwise required and documented by the IEC/IRB. A SUSAR will be reported to regulatory authorities. Participating investigators and IEC/IRB will receive a SUSAR summary.

8.3.5. Pregnancy

All initial reports of pregnancy in participants, with onset after the PP1 visit, must be reported to the sponsor by the study site personnel within 24 hours of their knowledge of the event using the appropriate pregnancy notification form. Abnormal pregnancy outcomes (eg, spontaneous abortion, fetal death, stillbirth, congenital anomalies, ectopic pregnancy) are considered SAEs and must be reported using an SAE reporting form. Any participant who becomes pregnant after the PP1 visit will not be eligible to receive the booster vaccination. These participants will remain in the study and will continue to undergo all procedures for surveillance and follow-up of COVID-19, immunogenicity and safety as outlined in the protocol for all participants.

8.3.6. Adverse Events of Special Interest

AESIs are significant AEs that are judged to be of special interest because of clinical importance, known class effects, or based on nonclinical signals. AESIs will be carefully monitored during the study by the sponsor. Participants will be reminded daily within the 30 day time period post-vaccination via eCOA diaries if they have experienced any health concerns (including new onset of symptoms such as shortness of breath, chest pain, leg swelling, persistent abdominal pain, severe or persistent headaches or blurred vision, easy bruising, or tiny blood spots under the skin beyond the site of the injection) related to suspected AESI's post-vaccination, and if so, participants will be advised to contact the study center.

AESIs must be reported to the sponsor within 24 hours of awareness irrespective of seriousness (ie, serious and non-serious AEs) or causality following the procedure described above for SAEs.

Specific requirements for the AESI are described below.

8.3.6.1. Thrombosis with Thrombocytopenia Syndrome (TTS)

As described in Section 2.3.1, Risks Related to Study Participation, TTS has been observed very rarely following vaccination with Ad26.COV2.S and is considered to be an AESI in this study. TTS is a syndrome characterized by a combination of both a thrombotic event and thrombocytopenia.

Because this syndrome is rare and not completely understood, all cases of thrombosis and/or thrombocytopenia will be considered a suspected case of post-vaccination TTS until further adjudication can be performed. An AESI Adjudication Committee with appropriate expertise will be established to evaluate each suspected AESI and determine whether it is a case of post-vaccination TTS. The investigator shall be responsible for reporting any suspected AESI of post-vaccination TTS using the SAE form and the form detailed in Section 10.11, Appendix 11: A suspected TTS case is defined as:

- Thrombotic events: suspected deep vessel venous or arterial thrombotic events as detailed in Section 10.12, Appendix 12 OR,
- Thrombocytopenia, defined as platelet count below 150,000/ μ L (Brighton Collaboration, Interim Case Definition 2021) post-vaccination

Symptoms, signs, or conditions suggestive of a thrombotic event should be recorded and reported as a suspected AESI even if the final or definitive diagnosis has not yet been determined, and alternative diagnoses have not yet been eliminated or shown to be less likely. Follow-up information and final diagnoses, if applicable, should be submitted to the sponsor as soon as they become available.

In the event of thrombocytopenia post-vaccination, study site personnel should report the absolute value for the platelet count and the reference range for the laboratory test used.

In the event of a thromboembolic event or suspected TTS post-vaccination, serum samples obtained both pre- and pos-vaccination should be retrospectively analyzed by the central laboratory for the presence of coagulation factors; repeat testing may be requested for confirmation upon sponsor discretion.

Suspected AESIs will require enhanced data collection and evaluation (see Section 1.3.6). Every effort should be made to report as much information as possible about the AESI to the sponsor in a reasonable timeframe.

If an event meets the criteria for an SAE (Section 10.4.1), it should be reported using the same process as for other SAEs.

The form detailed in Section 10.11, Appendix 11 is intended as a guide for assessment of the AESIs to facilitate diagnosis and determine treatment options. If the investigator is not the treating physician, every effort should be made to collect the information requested in the form from the treating physician and enter the available information in the eCRF. The sponsor will also attempt

to collect information from any thrombotic event, thrombocytopenia, or TTS reported prior to the current protocol Amendment 3.

